## 9. Data Management

In principle, the Sponsor and the initiating unit are jointly responsible for data management and analysis in the clinical study. In this study, data management will be carried out by the data management specialist from the CRO with the approval of the Sponsor. The data management specialist will develop the Data Management Plan (DMP) according to the project requirements and carry out data management based on the DMP to ensure the authenticity, integrity and traceability of clinical study data.

### 9.1 Original Documentation Forms

The original materials can prove the authenticity of the patients and the integrity and authenticity of the data. All data recorded in the electronic data capture (EDC) system are derived from the original data and should be consistent with the original materials. If the data in EDC system is inconsistent with the original materials, it is necessary to make modifications according to the original materials or provide reasonable explanations. The original materials are stored in each study site. The original materials include but are not limited to the following documents:

- Outpatient medical records and medical records for HD treatment;
- HD (filtration) treatment record sheets;
- Laboratory test reports;
- Other medical examination reports;
- ICFs;
- Medical device use records, etc.

## **9.2 Electronic Data Capture System**

In this study, data will be collected by using an EDC system, which is well validated to enable preservation of audit trails and good management of accounts and authorities.

The EDC system will automatically retain the audit trail of data, including the time of data entry and change, operator, data operator's name, reason for change, data value before the change, and data value after change, so as to ensure the traceability of data.

The system administrator creates accounts for different roles, grants different access permissions, and strictly manages and controls the application and cancellation of accounts.

## **9.3 Design of Electronic Case Report Form**

The data management specialist firstly designs the eCRF according to the study protocol and the Clinical Data Acquisition Standard Harmonization (CDASH), and then the database designer establishes the eCRF in EDC and sets the procedure for logic verification of the data to be collected; The database can be only launched upon the test by the data management specialist.

## **9.4 Electronic Case Report Form Completion**

The eCRF will be completed by the investigator or authorized clinical research coordinator (CRC) according to the source documents (including original medical records, examination reports, etc.). The investigator is responsible for timely and accurately entering the study data into the EDC system. The clinical research associate (CRA) approved by the Sponsor is responsible for confirming that all data records and reports are correct and complete, and that all data in the EDC system are consistent with the original materials.

## **9.5 Data Verification and Query Management**

The reliability, completeness and accuracy of data in the EDC system will be verified according to the Data Verification Plan (DVP) which mainly includes logic verification and manual verification. Data entry into the EDC system will be performed by the investigator or the staff designated by the investigator with their accounts. The data management specialist is responsible for data validation. If questionable data are found, queries could be raised in the system. The investigator or the staff designated by the investigator will verify and correct the data or respond to the queries. All data modifications would have modification trace in the system. If CRA may also raise queries in the system if questionable data are found when performing source data verification (SDV).

## **9.6 Medical Monitoring**

Medical monitoring will be completed by the medical monitor throughout the study, including but not limited to review of eligibility, protocol violations, periodic clinical study data, and treatment data.

## **9.7 Data Quality Assurance**

This study will use quality control and data validation processes to ensure the reliability and accuracy of the clinical database. The Monitoring Plan and DMP will detail the data entry, verification, clarification and validation processes to be followed by all relevant study personnel

---

to ensure compliance with Good Clinical Practice.

## **9.8 Data Management Plan**

The medical coder will be responsible for medical coding in this study. The MedDRA will be used for coding of AEs and past medical history, while WHO (World Health Organisation) Drug Dictionary will be used for that of concomitant medications. The medical coding will follow the *Medical Coding Plan*, which specifies in detail the contents of medical coding entries, dictionary version, dictionary update, coding review, etc.

## **9.9 External Data Management**

The external data for this study are test results from the central laboratory and will be managed according to the External Data Transmission Agreement.

## **9.10 Blind Review**

Before locking the clinical study database, the Sponsor's representative, PI, statistical analyst and data management specialist blindly review the data, jointly review the questionable data, divide the statistical analysis population according to the clinical study protocol and sign the decision on the division of the statistical analysis population.

## **9.11 Database Locking**

After all the queries are answered and the data in the database are confirmed to be complete and accurate, the database will be locked by the database management specialist with the joint approval of the Sponsor's representative, PI, statistical analyst and data management specialist.

## **9.12 Submission and Archiving of Data Management Documents**

After the database is locked, the data administrator shall write Data Management Report based on the actual implementation of the project, and complete the submission and archiving of paper and electronic documents according to the project document management requirements.

The data management specialist submits the data to the statistical analyst. The statistical analyst will perform statistical analysis according to SAP.

# **10. Feasibility Analysis**

## **10.1 Analysis of the Possibility of Success**

- (1) This study will be conducted in accordance with the study protocol developed in accordance with the Declaration of Helsinki (the 64th WMA General Assembly, Fortaleza, Brazil, October 2013), the *Good Clinical Practice for Medical Devices (GCP)* (CFDA, NHFPC Order No. 25), the *Provisions for Medical Device Registration* (CFDA Order No. 4) and other relevant regulations.
- (2) The Ethics Committee of the initiating unit is responsible for reviewing the ethics and scientificity of the study protocol. The Ethics Committee of each clinical study institution reviews the feasibility of the study, the qualification and experience of the investigators, and the equipment and conditions. Patients will be recruited volunteers who understand the objectives of the study and have adequate compliance with the study protocol. By

---

signing the ICF, the rights and interests of the patients will be fully guaranteed, which provides a guarantee for the completion of the clinical study.

- (3) Before the start of this study, the Sponsor or its designee will conduct unified training on the investigational medical device, study protocol and study-related data, unified recording method and evaluation criteria for the relevant personnel participating in this clinical study.
- (4) Theranova 400 has been marketed in 44 countries or regions around the world with more than 3.5 million devices used, and some clinical efficacy and safety data have been accumulated. Moreover, its composition structure and technical standards comply with the requirements of relevant national and industry standards, and all the technical requirements for product safety and performance have passed the relevant tests by Guangdong Medical Device Quality Supervision and Inspection Institute.
- (5) The participating units of this clinical study are qualified as national clinical study institutions for drugs/medical devices, and have rich clinical study experience and good quality control system.
- (6) All the staff participating in this study have received unified training and have a high standard of GCP regulations, which can ensure that all the original data such as observation results and laboratory tests in the clinical study are carefully recorded and verified, and finally ensure that all the conclusions drawn after the completion of the clinical study are derived from the real original data.

In summary, the success of this clinical study is highly controllable.

## 10.2 Analysis of the Possibility of Failure

- (1) Failure to strictly implement the clinical study protocol, failure to operate, inspect and evaluate in accordance with the specifications, failure to reach approximately 308 valid cases and other factors may cause the failure of this study, but these factors are still controllable.
- (2) The patients enrolled in this study are patients with chronic kidney failure requiring HD/HDF treatment. The patient may have other complications. The improvement of various indicators after treatment is related to the patient's underlying diseases and treatment compliance, not completely dependent on the investigational product. During this study, the investigator will complete the relevant examinations according to the requirements of the protocol, strictly implement the inclusion and exclusion criteria of cases and carry out the treatment in strict accordance with the requirements of the protocol, avoiding the inclusion of patients who cannot finish the expected treatment and have poor compliance, so as to reduce the interference factors as far as possible.
- (3) The investigators participating in this clinical study shall be trained in product knowledge and operating procedures by the personnel designated by the Sponsor to ensure that the treatment operators are skilled. During the operation, the occurrence of AEs will be closely observed and a detailed treatment plan will be developed to prevent the occurrence of AEs.

---

In conclusion, this clinical study is less likely to fail.

## **11. Quality Control of Clinical Study**

### **11.1 Site Quality Control**

In order to ensure the quality of the study, the PIs participating in the study jointly discuss and develop the clinical study protocol before the study is officially initiated.

The Sponsor or person who's assigned shall organize the trainings on relevant laws and regulations, study protocol, principle of the investigational medical device, scope of application, product performance and treatment instructions for the personnel participating in the clinical study prior to the initiation of the clinical study, so as to improve each participant's understanding of relevant laws and regulations, study protocol and investigational medical device and to master and strictly implement the clinical study protocol to ensure the study quality.

It is necessary to ensure the accuracy, consistency, completeness and credibility of the data collected during the study. All the observed results and abnormal findings in clinical studies shall be timely and carefully verified and recorded to ensure the reliability of data. During the clinical study, the study site and central laboratory should provide laboratory qualification certificates (such as inter-laboratory quality assessment certificate) for regular quality control.

### **11.2 Monitoring**

The CRA approved by the Sponsor shall perform regular and irregular monitoring during the study. The CRA shall fulfill the responsibilities specified in GCP and be responsible for monitoring whether the study personnel follow the study protocol and accurately record the study results; During each monitoring, the CRA must compare the eCRFs with original CRFs and inform the investigator of any omissions or errors. Moreover, the CRA should also verify that all AEs are recorded and that SAEs or device deficiencies are reported and recorded within the required time. The CRA should submit a written report to the Sponsor in a timely manner after monitoring.

### **11.3 Audit and Inspection**

The study site must also be subject to audits by auditors appointed by the Sponsor in accordance with GCP requirements. The auditors conduct systematic and independent inspection on clinical study-related activities and documents to evaluate and determine whether the study is conducted in accordance with the study protocol, standard operating procedures and relevant regulatory requirements, and whether the study data are recorded in a timely, true, accurate and complete manner. The audit does not directly involve the personnel conducting the clinical study.

The regulatory authority may inspect the documents, facilities, records and other aspects related to the clinical study.

## **12. Ethical Review and Informed Consent**

### **12.1 Ethical Considerations**

---

- (1) Ethical review and informed consent are the main measures to ensure the rights and interests of patients. The parties participating in this study shall assume corresponding ethical responsibilities according to their responsibilities in the study.
- (2) This clinical study conforms to the ethical principles in the Declaration of Helsinki (the 64th WMA General Assembly, Fortaleza, Brazil, October 2013) and GCP and other relevant regulations, and the clinical protocol has been designed with full consideration of the rights and interests of patients.
- (3) The Ethics Committee of a medical device clinical study institution shall be composed of at least 5 members, including medical professionals and non-medical professionals, of which there shall be members of different genders. At least one of the non-medical professional members is a legal worker and one is a person other than the site. The members of the Ethics Committee shall have the qualification or experience in assessing and evaluating the science, medicine and ethics of the clinical study. All the members shall be familiar with the ethical guidelines and relevant regulations for medical device clinical studies and abide by the articles of association of the Ethics Committee.
- (4) Before the start of the study, the study protocol, ICF, patient recruitment procedures, and other written documents provided to the patients should be reviewed and approved by the Ethics Committee. Any amendment to the above documents should be re-approved by the Ethics Committee. The investigator may start screening a patient only after the written approval of consent has been given by the Ethics Committee.

## 12.2 Informed Consent

Before a patient participates in the study, the investigator should fully explain the details of the clinical study to the patient or the guardian of the patient with no or limited civil capacity, including known and foreseeable risks and possible AEs.

The patient or his/her guardian shall sign and date the ICF upon the investigator's full and detailed explanation, and the investigator shall also sign and date the ICF. For the incapacitated patients, if the Ethics Committee agrees in principle and the investigator believes that the patients' participation in the clinical study is in their own interests, they may participate in the clinical study upon the signature of their guardians before the study. If either the patient or his/her guardian cannot read, a witness should be present in the process of being informed. If important information or unexpected clinical effect involving the investigational medical device is found, the investigator and Sponsor should modify the Informed Consent Form. After the revised Informed Consent Form is approved by the Ethics Committee, the affected patients or their guardians should sign for confirmation again. A copy of the signed and dated Informed Consent Form shall be kept by the investigator and patient, respectively.

By signing the Informed Consent Form, the patient agrees the CRA/Auditor/Ethics Committee/regulatory authorities to verify the obtained original data of the clinical study to determine the reliability of such data.

## 13. Provisions for Reporting Adverse Events and Product Complaints

### 13.1 Adverse Events

### 13.1.1 Definition of Adverse Events

**Table 1. Adverse Event Term Definitions**

Adverse Event (AE)	An AE is any untoward medical occurrence in a clinical study and which does not necessarily have to have a causal relationship with the investigational medical device Chinese medical device GCP Article 93
Serious Adverse Event (SAE)	An SAE is any untoward medical occurrence in the clinical study that is life-threatening or leads to serious deterioration in health including: Fatal illness or injury; Persistent impairment of any body structure or body function; Hospitalization or prolongation of existing hospitalization; Medical or surgical intervention to preclude permanent impairment to any body structure or body function; Fetal distress, fetal death, or congenital abnormalities, congenital defects and other events. Chinese medical device GCP Article 93
Device Deficiency (DD)	DDs refer to unreasonable risks of medical devices under normal use during the process of clinical trial that may endanger human health and life safety, such as label error, quality problem and fault. Chinese medical device GCP Article 93

### 13.1.2 Safety Reporting

All AEs observed by the study personnel or reported by the patient during the course of the study will be documented from the time of signing the ICF (i.e., enrollment) through the final assessment visit (i.e., End of Study Visit). All device deficiencies (DD) observed by the study personnel or reported by the patient during the treatment period will be documented.

Any medical condition that is present at the time that the participant is screened will be considered medical history and not recorded as an AE or SAE. However, if the study participant's condition deteriorates at any time during the study, it will be recorded as an AE or SAE in the eCRF.

If a definitive diagnosis has been medically established by the physician caring for the patient or by the investigator, this diagnosis should be recorded as the AE or SAE. If a definitive diagnosis has not been medically established, the signs and symptoms should be recorded as the AEs or SAEs. Once the diagnosis is confirmed, the eCRF should be updated from signs and symptoms to the diagnosis.

If a patient is given a diagnosis and also experiences a complication of the diagnosis (e.g., myocardial infarction with congestive heart failure), both the diagnosis and the medical complication should be collected and recorded as separate events.

---

Adverse events or SAEs that change in severity will be documented only once with the highest degree of severity.

An elective procedure/surgery that occurs during the course of the study but is being performed for a documented pre-existing condition and was pre-planned prior to study entry will not qualify as an AE or SAE. If, however, the pre-existing condition unexpectedly deteriorates during the study requiring the procedure/surgery to be performed earlier than planned, the condition for which the procedure/surgery is being performed will qualify as an AE or SAE (refer to Table 1).

Laboratory and vital sign abnormalities qualify as AEs if medical intervention is required to treat or address the abnormality, if the patient must be discontinued from the study due to the abnormality, or if the investigator determines the value is clinically significant.

For all AEs associated with patients, a full description of the event should be recorded in the eCRF including the date and time of onset (when the signs and symptoms of the event began), outcome, seriousness, severity, event description, actions taken, and causal relationship of the AE or SAE. Investigators should review and reference the severity (refer to Table 2) and causality definitions (refer to Table 3) when determining relationship of the AE or SAE to the study device and procedure. The investigator may also discuss the event(s) with the Sponsor's Medical Monitor or designee.

For all AEs associated with users or other persons (not the study patient), a full description of the event should be recorded on the paper AE form and sent via email to Sponsor designee and Baxter Global Patient Safety Medical Device Vigilance

[REDACTED].

All AEs and SAEs should be actively solicited and documented in the eCRFs, no matter how common they are for a patient and regardless of the causality assigned by the investigator. Additionally, any AE and SAEs voluntarily reported by the patient should be recorded in the eCRF and verified by the investigator or designee with the relevant source documents.

The outcome/resolution of all AEs and SAEs will be determined by the investigator and documented in the eCRF. Investigators will follow all unrelated AEs and SAEs until resolution, stable, or the end of the study, whichever occurs first, and follow all study device-related and procedure-related AEs and SAEs until resolution or stable, including following the patient after the end of the study if necessary. Outcomes and other relevant information obtained after the end of the study will be reported via the paper AE form and sent via email to Baxter Global Patient Safety Medical Device Vigilance [REDACTED].

For the outcome categories that can be used in the eCRF by the investigator refer to Table 4.

During the study period, if a patient experiences an AE which is considered causally related to a Baxter medicinal/drug product (not the study medical device or comparator), the event shall be forwarded by the investigator or designee within 24 hours of becoming aware of the AE to Baxter

Global Patient Safety [REDACTED] for assessment as per Baxter's process for case processing of spontaneous reports.

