### **7.1.7.2 Method for Evaluation, Recording and Analysis of Safety Endpoints and Time Selection**

#### **7.1.7.2.1 Method for Evaluation and Recording and Time Selection**

##### **(1) Endpoints:**

- 1) Adverse events (AEs) and SAEs: All AEs and SAEs occurring in the duration of ICF signing and the end of the trial will be recorded, and SAEs will be reported according to regulatory requirements;
- 2) C-reactive protein (CRP): Blood will be taken for testing before the mid-week treatment day dialysis session
- 3) Blood routine, electrolytes :
  - Blood routine: Hematocrit, hemoglobin , mean corpuscular hemoglobin , mean corpuscular hemoglobin concentration , mean corpuscular volume , platelet count, red blood cell count, white blood cell count, percentage of eosinophils;
  - Blood electrolytes: Phosphorus (P), potassium (K), sodium (Na), calcium (Ca), chlorine (Cl).

Blood will be taken for testing before and after the dialysis treatment at the mid-week treatment day dialysis session;

- 4) Liver function: Blood will be taken for testing before the dialysis treatment at the mid-week treatment day dialysis session;
- 5) Collecting vital signs (according to various standard operation procedure):
  - Blood pressure (BP), pulse rate: Before and after the mid-week HD treatment
  - Respiratory rate and body temperature: Before the mid-week HD treatment;
- 6) Device deficiencies (DDs) (during use of the investigational product; which would include functional characteristics [e.g., leaks, tubing separations, etc.]). All DDs occurring in the treatment period will be recorded.

[figure not shown]

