### 8.7.1.3 Analysis of Safety Endpoints

Safety endpoints will be evaluated as follows:

1. The summary of AEs will include AEs that occur on the day of or after the study treatment. Pre-treatment AEs including AEs reported at Screening and Randomization will be recorded in the eCRF but will not be summarized in the safety tables. Adverse events will be mapped to a Primary System Organ Class (SOC) and Preferred Term (PT) according to Medical Dictionary for Regulatory Activities (MedDRA) and summarized descriptively by SOC, PT and treatment group. Treatment group comparability in the incidence of AEs will be evaluated using Fisher's exact test. An overview (overall) summary table of all AEs will be generated that includes the total number of AEs, number and percentage of patients with at least one AE, number and percentage of patients with at least one SAE, number and percentage of patients with at least one severe AE, number and percentage of patients with at least one AE probably associated with study treatment, number and percentage of patients with an AE leading to study discontinuation and number and percentage of patients with an AE leading to death. This summary will be presented by treatment group and combining both groups (Total). In addition, two separate AE summary tables will be provided, one for analysis by severity and relationship to the study dialyzer, and the other will provide a separate AE summary table for SAEs and AEs that led to withdrawal from the study.
2. Device deficiencies (DD) will be summarized descriptively.
3. Serum chemistry, hematology assessments, liver function, patient vital signs, and CRP will be summarized descriptively per measurement time point using n, mean, median, standard deviation, minimum, and maximum.

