### **7.2 Baseline**

Unless otherwise specified, baseline is defined as the last non-missing measurement (including unscheduled assessments) taken prior to the first application of study device. In the case where Adverse Events (AEs) and medications without onset time record commencing on the reference start date will be considered post-baseline.

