## 18.2 Adverse Events

An AE is any untoward medical occurrence in a clinical study and which does not necessarily have to have a causal relationship with the investigational medical device *Chinese medical device GCP Article 93*. Adverse Events (AEs) will be coded using MedDRA and presented by System Organ Class (SOC) and Preferred Term (PT). Treatment-emergent AE (TEAE) will include AEs that occur on the day of or after the study treatment and will be summarized in the safety summaries. Pre-treatment AEs including AEs reported at Screening and Randomization will be recorded in the eCRF but will not be summarized in the safety summaries.

In AE summaries, the primary system organ class will be presented alphabetically and the preferred terms will be sorted within primary SOC in descending frequency. The sort order for the preferred term will be based on their frequency. Treatment group comparability in the incidence of AEs will be evaluated using Fisher's exact test.

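### An adverse event that starts after screening but before the study day, and worsens during or after the session, drops out of the AE summaries because the treatment-emergent definition has no worsening clause

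*Protocol*

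**What the plan says.** **Recording.** AEs are collected from consent (protocol 7.1.7.2.1 and 13.1.2). Each record carries "the date and time of onset (when the signs and symptoms of the event began". On events that change, 13.1.2 says: "Adverse events or SAEs that change in severity will be documented only once with the highest degree of severity". The same section treats a condition already present at screening as medical history, but has it recorded as an AE if it deteriorates during the study.

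**Summarising.** Protocol 8.7.1.3: "The summary of AEs will include AEs that occur on the day of or after the study treatment". SAP 18.2: "Treatment-emergent AE (TEAE) will include AEs that occur on the day of or after the study treatment". SAP 18.2 adds: "Pre-treatment AEs including AEs reported at Screening and Randomization will be recorded in the eCRF but will not be summarized in the safety summaries". Both sections compare AE incidence between groups with Fisher's exact test.

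**Timing on the study day.** SAP 7.1 sets the reference start as a day, not a clock time. SAP 7.2 says that AEs and medications "without onset time record commencing on the reference start date will be considered post-baseline".

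**The concern.** A treatment-emergent definition normally has two limbs: events that start after exposure, and events that started earlier but got worse after it. This plan has only the first. Combined with the one-record rule, a mild event arising between screening and the study day that becomes severe or serious during the session keeps its pre-treatment onset and is never tabulated.

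The AE tables are the trial's main comparative safety output, and the results support a registration application (protocol section 4). If the session aggravates an existing event, that is something those tables should show.

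A lesser problem concerns the study day itself. Blood samples and vital signs are taken before dialysis that day, and under 13.1.2 a clinically significant abnormality is an AE. The calendar-day wording can be read to count such a finding as emergent even when its recorded time precedes exposure.

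**Working it through.** The plan has no figure to reproduce here. The check applies the stated rules to each possible timing.

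Inputs:
1. Onset is the start of signs and symptoms, with date and time recorded (protocol 13.1.2).
2. A change in severity does not create a new record (protocol 13.1.2).
3. An AE is summarised if it occurs on or after the study day; pre-treatment AEs are recorded but not summarised (protocol 8.7.1.3, SAP 18.2).
4. Deterioration of a condition present at screening is recorded as an AE (protocol 13.1.2).
5. Only untimed AEs on the reference date are assigned to post-baseline by default (SAP 7.2).

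| Case | Record | In the AE summaries and Fisher's test? |
|---|---|---|
| A. Present at screening, deteriorates in or after the session | Recorded as an AE on deterioration | Can be included |
| B. Starts after screening and before the study day, ongoing, worsens or becomes serious in or after the session | One record, original onset, highest severity | No |
| C. Starts on the study day, timed before dialysis | One record with onset time | Unsettled |
| D. Starts on the study day, no time recorded | One record | Yes, by the SAP 7.2 default |
| E. Starts during or after the session | One record | Yes |

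**Case B.** Could an ongoing AE be said to occur on the study day and so be included? SAP 18.2 closes that route: AEs reported at screening and randomisation are named as pre-treatment and kept out of the summaries. Input 4 does not help, because it covers only conditions present at screening. So worsening of medical history can be tabulated, while worsening of an AE that arose after screening cannot. The plan gives no reason for the difference. The raised severity is stored, but the items listed for the AE record in 13.1.2 include no date for a change in severity; only the event description might show when it happened.

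**Case C.** The calendar-day wording points to inclusion. Two things point the other way. An AE timed before dialysis is, in ordinary language, a pre-treatment AE. And a default for untimed AEs has a purpose only if a recorded time would otherwise decide. The emergent definition in SAP 18.2 does not take that up, so the passages disagree.

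**Size.** The number of Case B events depends on the rate of new AEs between screening and the session, the share still ongoing, and the share that worsen. The documents give none of these, so no count can be derived.

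**The case against.** The strongest reply is that the gap is narrow and the events are not lost. Much of this stands.

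- Case B needs an AE that is new since screening, unresolved at the session, and then worse within the short follow-up, which covers the treatment day and the day after (protocol 7.2.1.4). A complication of a diagnosis is already a separate event under 13.1.2.
- Every AE is recorded, and SAP 18.2.1 lists them all. SAP 18.2.2, 18.2.6 and 18.2.8 list AEs leading to withdrawal, serious AEs and AEs leading to death. Protocol 13.1.2.1 requires SAEs to reach the sponsor within 24 hours. A reader might infer that a serious worsening could go unseen; the documents do not support that. What is lost is its place in the summaries and the test.
- There is no safety hypothesis, margin or alpha, and randomisation should make misclassification broadly similar in the two arms. No directional bias is shown.

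Three stronger readings are tempting and should not be drawn.

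- That every AE timed before dialysis on the study day is counted as emergent. No passage says so; the wording is ambiguous.
- That every study-day AE based on CRP or liver function must precede exposure. Protocol 7.1.7.2.1 and the schedule place those samples before dialysis only, for example "C-reactive protein (CRP): Blood will be taken for testing before the mid-week treatment day dialysis session". Protocol 7.2.1.3, however, has the visit items, which include both tests, collected before and after dialysis.
- That the length of the pre-session window measures the problem. Screening of up to 14 days plus up to 14 days from randomisation gives 28 days, or about 21 days if the three-week maximum per patient in protocol 7.1.5.7 governs. Neither says how many AEs are ongoing or worsen, so a ratio of windows is not an effect size.

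None of this supplies the missing worsening clause.

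**Conclusion.** The concern holds for one defined group: AEs that begin after screening and before the study day, are still ongoing, and worsen or become serious during or after the session. Under the plan as written they are left out of the AE summaries and the Fisher comparison. This rests on the one-record rule keeping the original onset, which is how 13.1.2 defines onset, and on the explicit exclusion of pre-treatment AEs.

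Classification of study-day AEs timed before dialysis is a separate inconsistency between SAP 7.2 and the calendar-day wording of SAP 18.2 and protocol 8.7.1.3. It needs reconciling, but it is not a demonstrated overcount.

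The number of events affected cannot be computed and may be small. The primary non-inferiority analyses and the sample size are unaffected. The change is still worth making: the rule misclassifies these events whenever they occur, and in an open-label trial such cases are better settled by rule than one at a time.

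**What to change.** 1. **SAP 18.2 and protocol 8.7.1.3.** Define a treatment-emergent AE as one whose onset date and time are at or after the start of the study session, or one that began earlier and increased in severity or became serious at or after that start. Keep the SAP 7.2 default that an untimed AE on the study day counts as post-baseline. This also resolves the same-day ambiguity.
2. **Protocol 13.1.2.** Where an AE began before the session and worsens after it, enter the worsening as a new record dated at the worsening. Apply the once-only, highest-severity rule separately within the pre-session and post-session periods.
3. **eCRF completion guidance.** Add a matching instruction.

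Cost: a few extra AE records, and a wording amendment to the protocol that needs Ethics Committee approval before it is implemented (protocol 14.3). No new timing item is needed, since the AE description is already specified as "including the date and time of onset".
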